Finally, regarding the safety of platelet-rich plasma, it has been shown to be a safe product in multiple clinical trials. A recent Chocrane meta-analysis evaluated the adverse effects and complications of PRP in 19 clinical trials (1088 patients).¹⁷ This study included patients who had undergone surgery for multiple orthopedic conditions including rotator cuff tears, anterior cruciate ligament tears, Achilles and patellar tendinopathy, and epicondylitis. The percentage of complications associated with treatment was 1.1% (12/1088 patients). In 15 of the 19 clinical trials there were no adverse effects or complications related to PRP. Reported complications were generally mild, including injection site hyperesthesia, local edema, and superficial injection site infections. No severe complications associated with the procedure were reported in any of the 1088 patients.¹⁷

The purpose of this study is to perform a double-blind randomized controlled trial, comparing PRP with corticosteroids to provide pain relief and improve function in patients with rotator cuff tendinopathy. The hypothesis of this study is that PRP would provide improved pain relief and function in patients with rotator cuff tendinopathy compared to standard treatment of CS injections.

Hypothesis

In patients with rotator cuff tendinopathy, PRP subacromial injections produce significantly greater improvement in shoulder pain and function than standard treatment with corticosteroid subacromial injection.

Goals

primary objective

To evaluate in patients with rotator cuff tendinopathy whether a subacromial infiltration with PRP produces a significant improvement in pain (measured through the visual analogue scale (VAS) for pain) compared to a control group treated with standard corticosteroid therapy.

secondary objective

2. To assess whether the use of PRP applied as a subacromial infiltration in patients with rotator cuff tendinopathy improves the functional **results** (measured using the American Shoulder and Elbow Surgeons (ASES) score)¹⁸ and Constant's score,¹⁹ compared to a control group that underwent subacromial infiltration with corticosteroids.

3. To assess whether the use of PRP applied as a subacromial infiltration in patients with rotator cuff tendinopathy improves the sleep **disorders** (measured using the Pittsburgh score)²⁰ compared to a control group that underwent subacromial infiltration with corticosteroids.

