Variables to be measured and data documentation

All the variables to be measured will be recorded in a RedCap database specially designed for this clinical trial.

A) Demographic and related to the injury.

They will be recorded by the principal investigator 24-48 hours prior to the infiltration.

- Sex: male - female
- Age: Age in years on the day of infiltration
- Smoking: yes-no

B) Cynic variables

Pre-infiltration evaluation: It will be in charge of the principal investigator and it will be carried out 24-48 hours before the infiltration in the orthopedics office.

In it will be evaluated:

clinical variables: Mobility - Pain - Functional Scores (ASES - Constant) - Sleep disorders (Pittsburgh Score)

Imaging variables: Chronic tendinopathy will be defined as the presence of a hyperintense signal in the supraspinatus on magnetic resonance imaging (carried out a maximum of 6 months prior to clinical diagnosis), with the absence of partial or total ruptures of the tendon or as the presence of a hyperechoic signal in the supraspinatus. supraspinatus with increased intratendon Doppler flow. The presence of the tendinopathy will be confirmed by ultrasound the week prior to the infiltration to rule out the progression of the tendinopathy to a partial rupture of the tendon and to evaluate the presence of flow within the supraspinatus as a sign of tendinopathy with echodoppler.

Post-infiltration evaluation:

In it will be evaluated:

clinical variables: Mobility - Pain - Functional Scores (ASES - Constant) - (Pittsburgh Score) at one month, 3 months and 6 months postinfiltration. It will be in charge of the Shoulder Fellow who will not know to which branch of treatment the patient was assigned. That is to say it will be *blinded to intervention*.

Imaging variables: The presence of vascular flow within the tendon will be measured in the musculoskeletal ultrasound 6 months after the infiltration in the usual way. It will be in charge of a doctor specialized in musculoskeletal ultrasound who does not will know to which treatment arm the patient was assigned. That is to say it will *beblinded to intervention*.

The variables that will be evaluated are described below:

- Mobility: *The 4 mobility parameters will be measured in degrees with a goniometer*
 - Anterior flexion
 - Abduction
 - External Rotation with the arm at 90⁰of abduction
 - Internal Rotation with the arm at 90⁰of abduction

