In the event that the patient presents a complication, they will have the contact number of the principal investigator to be attended by him or by a surgeon from the team in the orthopedic clinics or on duty at the Italian Hospital of Buenos Aires. Likewise, the doctors on duty will be informed about the development of the following protocol in order to notify the principal investigator or a member of the team in the event that a patient presents any post-infiltration complication.

Scheme of the evaluation points in time, responsible for the evaluation and the variables that will be recorded

	pre-infiltration (24-48 hours prior)	1 month post-infiltration	3 months post-infiltration	6 months post-infiltration
Evaluator	Principal investigator	Shoulder Fellow	Shoulder Fellow (clinical variables) Sonographer (imaging variables)	Shoulder Fellow (clinical variables)
Variables Clinics	-Demographic -Mobility -Pain -Functional Scores (ASES – Constant - Pittsburgh)	-Mobility -Pain -Functional Scores (ASES – Constant-Pittsburgh) -complications	-Mobility -Pain -Functional Scores (ASES – Constant-Pittsburgh) -complications	-Mobility -Pain -Functional Scores (ASES – Constant-Pittsburgh) -complications
Imaging variables	Magnetic nuclear resonance Ecodoppler musculoesquelético		Ecodoppler musculoesquelético	

Statistical analysis raised

Quantitative variables will be presented as mean and standard deviation or median and interquartile interval according to the observed distribution. Categorical variables will be presented as proportions. The 95% confidence intervals will be calculated for each of the estimators.

The comparison of continuous data between two groups will be analyzed with the t test if the distribution of the variables is normal or with the Mann-Whitney-Wilcoxon test if it is not. The analysis of categorical data will be carried out with the chi-square test. Statistical analysis will be performed with STATA MP version 16 (Stata Corporation, College Station, TX). A p value less than 0.05 will be considered statistically significant.

Sample size

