To calculate the sample size, the expected values of the variable "pain" represented by the VAS, which is the main outcome variable, are used. The minimal clinically relevant difference (MCID) was previously described in the setting of rotator cuff disease as 1.5 points with a standard deviation of 2.41 points on a 10-point scale for shoulder pain.²² We will work with a type I error probability of 5% and a power of 90%. Using these parameters in a superiority formula, a sample size of 45 patients per group was calculated. Considering the possibility of a loss to follow-up of 10% of the patients per group, 50 patients per group will be included, with a total final sample of 100 patients. The sample size was calculated using the formula of Fleiss et al.²³

Randomization

All included patients will be randomized after obtaining informed consent. Each patient will be randomly assigned a treatment arm using the online randomizer (<http://protocolos.hospitalitaliano.org.ar>) to treatment arms 1 (control) or 2 (intervention)

ethical considerations

Participation in the study will be in all cases voluntary and certified by the informed consent process. The study will be carried out in full accordance with current national and international regulations: Declaration of Helsinki of the World Medical Association, Provision 6677/10 of ANMAT, and the Standards of Good Clinical Practices ICH E6.

The proposed intervention does not frequently present adverse events and there are known contraindications for its application. The procedure will be paid for by the financing of the study, it will not imply any cost to the patient or their health coverage. The costs of monitoring and periodic evaluations will be borne by the study investigators.

All study data will be treated with the utmost confidentiality, with restricted access only to authorized personnel for the purposes of the study in accordance with current legal regulations National Law on Protection of Personal Data 25,326 (Habeas Data Law).

Damage or complications

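### The 45 per group rests on a one-sided 5% test that the plan never declares; read two-sided, power is about 83%, not 90%

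*Combined protocol and SAP*

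**What the plan says.** The Sample size section bases the calculation on VAS pain, the main outcome. It takes the minimal clinically relevant difference "as 1.5 points with a standard deviation of 2.41 points on a 10-point scale for shoulder pain". It then states "We will work with a type I error probability of 5% and a power of 90" per cent, and continues: "Using these parameters in a superiority formula, a sample size of 45 patients per group was calculated". Allowing for 10% loss to follow-up, this becomes 50 per group and 100 in total.

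The section headed Statistical analysis raised plans a t test, or a Mann-Whitney-Wilcoxon test if the data are not normal, for continuous outcomes, and chi-square tests for categorical ones. Its decision rule is "A p value less than 0.05 will be considered statistically significant". On estimation it says "The 95% confidence intervals will be calculated for each of the estimators".

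The Hypothesis section is worded in one direction: "PRP subacromial injections produce significantly greater improvement in shoulder pain and function than standard treatment".

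None of these sections, nor any other part of the document, says whether the primary test is one-sided or two-sided.

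**The concern.** The sample size and the analysis have to refer to the same test. The number of patients matches a one-sided 5% test. The analysis section, as most readers would take it, describes a two-sided 5% test. The two agree only under a declaration that neither contains.

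Two things are at stake. First, if the analysis is run two-sided, the stated 90% power is not what the trial has. Second, sidedness fixes the rejection region of the primary test. While it is undeclared, there is a range of results in which the trial is positive on one reading and negative on the other, and the choice could be made after the data are seen.

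**Working it through.** **Inputs, all from the Sample size section:** difference d = 1.5; SD = 2.41; type I error 0.05; power 0.90; equal groups; 10% loss. Not given: the number of tails.

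**Formula for two means, per group:** n = 2 × SD² × (z_α + z_β)² / d².

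The common factor is 2 × 2.41² / 1.5² = 11.6162 / 2.25 = 5.1628, and z_β = 1.2816.

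**Reproducing the plan's figure**

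| Reading | z_α | (z_α + z_β)² | n, normal formula | n, noncentral t |
|---|---|---|---|---|
| One-sided 5% | 1.6449 | 8.564 | 44.21, so 45 | 45 |
| Two-sided 5% | 1.9600 | 10.507 | 54.25, so 55 | 56 |

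The plan's 45 is the one-sided value. Two-sided at 80% power gives 41 and one-sided at 80% gives 32, so a different power target from among the usual ones does not explain it. The loss allowance is correct: 45 / 0.9 = 50.

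**Power at the planned size, for a true difference of 1.5 points**

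| Evaluable per group | One-sided 5%, t test | Two-sided 5%, t test | Two-sided 5%, normal approximation |
|---|---|---|---|
| 45 | 90.1% | 83.1% | 83.9% |
| 50 (no losses) | 92.6% | 86.9% | 87.5% |

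Even with no losses, two-sided power stays below 90%.

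**Detectable difference.** With 45 per group and a two-sided t test, 90% power is reached at 1.67 points (1.665), above the 1.5 points on which the trial was sized.

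**If the Mann-Whitney test is used.** Assuming normal data and a relative efficiency of 0.955, the effective size is 45 × 0.955 = 42.98 per group. Power is then about 81% two-sided and about 89% one-sided.

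**Where the two readings give different verdicts.** The standard error is 2.41 × √(2/45) = 0.508. With 88 degrees of freedom the critical t values are 1.662 (one-sided) and 1.987 (two-sided). The critical observed differences, if the sample SD equals 2.41, are:

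- one-sided: 1.662 × 0.508 = 0.84
- two-sided: 1.987 × 0.508 = 1.01

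A result in favour of PRP between 0.84 and 1.01 points is significant one-sided, yet its 95% interval includes zero. With a true difference of 1.5 points, the probability of a result that is significant only one-sided is 90.05% − 83.15% = 6.9%. This is the power gap seen from another side, not an additional loss.

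**The case against.** The strongest reply is that nothing has been miscalculated. The 45 follows exactly from the stated inputs under a one-sided test, and the plan's language leans that way: the hypothesis is directional and the calculation is described as one for superiority. The sentence on 95% intervals closes the paragraph on descriptive summaries and is not tied to a decision rule, so the two-sided reading rests largely on convention. On this view the gap is one of reporting. Power of 83% to 87% is also respectable, and nobody is asking for more patients.

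Much of this is right. The calculation is internally correct on the one-sided branch, and the 83% depends on the two-sided reading. But superiority is also commonly tested two-sided, and a directional hypothesis does not declare a one-sided test. The analysis section applies a single unqualified threshold to t, Mann-Whitney and chi-square tests alike, which is the ordinary two-sided convention. Even on the one-sided branch the document needs an edit, because neither section declares the test and an ordinary 95% interval does not correspond to a one-sided 5% test. That 83% may be acceptable does not make 90% the correct figure to state.

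Two further points stand as limits. The power figures are for one comparison at one time, while pain is measured "at one month, 3 months and 6 months postinfiltration" and no primary time point is named. And if the Mann-Whitney test is used, power is slightly below the t-test figure on either branch.

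**Conclusion.** The concern holds. The sample size matches a one-sided 5% test that the plan does not declare. Under the usual two-sided reading of the analysis section, power at 45 evaluable per group is 83.1% rather than 90%, and the risk of missing a true 1.5-point difference is about 17% rather than 10%. Reaching 90% two-sided would take 55 to 56 evaluable per group. If a one-sided 5% test was intended, t-test power is 90.1% and the stated figure stands, but the declaration and matching intervals are still missing.

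These figures assume that 2.41 is the SD of the pain value actually analysed, that the groups are equal, and that one comparison is made at one time point without baseline adjustment. This should be corrected before the analysis, because it determines the rejection region of the primary test.

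**What to change.** Keep 100 patients and make two edits.

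1. In Statistical analysis raised, add that the primary test is two-sided at the 5% level.
2. In Sample size, replace the power statement with: 45 evaluable patients per group give about 83% power (two-sided 5%, t test) to detect 1.5 points with an SD of 2.41 in a single pre-specified comparison, and 90% power to detect about 1.67 points. For this sentence to be true, the plan must name that comparison, including its time point. It should also note that power is about 81% if the Mann-Whitney test is used on normal data.

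If the sponsor intended a one-sided 5% test, say so in both sections and replace the 95% interval for the primary comparison by a 90% two-sided interval or a one-sided 95% bound.

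If the sponsor wants to keep 90% power with a two-sided test, the cost is recruitment: 55 / 0.9 = 61.1, so 62 per group, or 56 / 0.9 = 62.2, so 63 per group, for 124 to 126 in total.

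The recommended route costs one added and one replaced sentence, plus naming the primary time point. It changes neither enrolment nor the analysis method. Its drawback is that the stated power becomes less favourable.

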Annex 1: Informed consent. (separate sheet)	
Annex 2: ASES Score	
Annex 3: Constant Score	
Appendix 4 : Pittsburgh Sleep Quality Index.	
Annex 5: Insurance for clinical trial	

Introduction

Rotator cuff tendinopathy represents the most common pathology of the shoulder, and is the main reason for outpatient consultation for pathologies related to the shoulder girdle.^{1,2} First-line treatment for rotator cuff tendinopathy usually consists of activity modification, stretching and strengthening exercises, oral anti-inflammatory medications.³⁻⁶ When these initial measures are not effective, a second line of treatment consists of local infiltrations with corticosteroids.³⁻⁶ Corticosteroid injections are often used as an inexpensive and effective treatment to reduce pain and improve movement. However, most of the studies evaluating the effectiveness of corticosteroids in patients with rotator cuff tendinopathy show that the clinical results are usually short-lived.⁶⁻⁷ In addition, corticosteroids do not have any biological effect that helps to regenerate or reverse the structural changes that occur in the rotator cuff tendons as a consequence of chronic inflammation.⁶⁻⁷

In this sense, platelet-rich plasma (PRP) emerges as a promising alternative due to its ability to release pro-regenerative growth factors (FsC) and cytokines at the lesion site (cite).⁸⁻⁹ Platelet Rich Plasma is considered a minimal handling product. It is commonly used in the United States, Europe and all of America. According to the FDA it falls within the scope of section 361 (Public Health Service Law, Code 21 of Federal Regulation 1271) of minimally manipulated therapies and according to ANMAT under law 16463 and decree 9763/64. In addition, the centrifuge that will be used in the following study at the Hospital Italiano de Buenos Aires is approved by the ANMAT in (RegenLab disposition 13735). Specifically, at the Hospital Italiano de Buenos Aires (HIBA), platelet-rich plasma has been used for more than 10 years for different musculoskeletal conditions, both on an outpatient basis or as an adjuvant to

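### The 10% loss allowance only adds patients; tests confined to those with a score at the visit can bias the comparison if loss depends on pain and differs between arms

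*Combined protocol and SAP*

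**What the plan says.** Loss to follow-up appears only under Sample size. The planning difference is introduced there in these words: "The minimal clinically relevant difference (MCID) was previously described in the setting of rotator cuff disease as 1.5 points". The other planning values are an SD of 2.41, 5% type I error and 90% power. From these, "Using these parameters in a superiority formula, a sample size of 45 patients per group was calculated". The allowance follows: "Considering the possibility of a loss to follow-up of 10% of the patients per group, 50 patients per group will be included".

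The section headed Statistical analysis raised is the whole analysis plan. It covers descriptive summaries, 95% intervals, chi-square for categorical data, a 0.05 threshold, and this rule for continuous outcomes: "The comparison of continuous data between two groups will be analyzed with the t test if the distribution of the variables is normal", with Mann-Whitney-Wilcoxon otherwise. It gives no analysis set, no statement that patients are analysed as randomised, no method for missing values, no model across visits and no sensitivity analysis.

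Pain, ASES, Constant and Pittsburgh scores are recorded before infiltration and at 1, 3 and 6 months after it (Schedule - masking - intervention, Stage 4; Variables to be measured and data documentation). The follow-up visits are counted from the infiltration, whereas randomisation takes place earlier, after consent. The Introduction says that most studies of corticosteroids in this condition "show that the clinical results are usually short-lived".

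**The concern.** Going from 45 to 50 per group protects precision. It does nothing about who is missing. A two-group test at one visit has to leave out anyone without a score at that visit, even when that patient's earlier scores are in the database.

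If patients in more pain are more likely to leave, the observed mean in an arm is too low. If this happens to a different degree in the two arms, the difference between them is wrong, and the 95% interval does not allow for it. Loss of painful corticosteroid patients would understate a PRP benefit; loss of painful PRP patients would overstate it.

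There is also a gap at the front. A randomised patient who is never infiltrated has no defined follow-up visits, and no rule says whether that patient is analysed. Without a rule, both matters can be settled after the results are known.

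**Working it through.** **1. The plan's own figures.** Normal formula: n = 2 × [(z_alpha + z_power) × SD / difference]².
- One-sided 5%, 90% power: 2 × [(1.645 + 1.282) × 2.41 / 1.5]² = 44.2, so 45 per group. This matches the plan.
- Two-sided 5%: 54.2, so 55 per group. This does not match. The unstated sidedness is a separate point.
- Loss allowance: 45 / (1 − 0.10) = 50. Correct as a count.

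**2. When bias arises.** Let d be the share lost in an arm and g the mean VAS of those lost minus that of those who stay. The observed mean in that arm is too low by d × g. The error in the difference (corticosteroid minus PRP) is d_PRP × g_PRP − d_CS × g_CS. It is zero when the two products are equal, for example 10% lost in both arms with the same g.

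**3. Size, if loss depends on recorded 3-month pain.** The SD of 2.41 is the plan's. The correlation r between visits (0.5 to 0.7) and the form of the dependence are assumptions, because the documents give neither. Month 6 is used for illustration. If m is the shift in mean 3-month VAS among those who stay, in SD units, the 6-month mean shifts by 2.41 × r × m.

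*Milder rule:* logistic, with the odds of leaving multiplied by 2.7 per SD of 3-month VAS. Numerical integration gives m = 0.047, 0.074, 0.108 and 0.133 at 5%, 8%, 12% and 15% loss.

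| Loss in the two arms | Difference in m | Bias at r = 0.5 to 0.7 | Share of 1.5 |
|---|---|---|---|
| 10% v 10%, similar patients | 0 | 0 | 0% |
| 12% v 8% | 0.034 | 0.04 to 0.06 | 3% to 4% |
| 15% v 5% | 0.0855 | 0.10 to 0.14 | 7% to 10% |

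*Upper-end rule:* the worst 10% at 3 months all leave, in one arm only. Then m = φ(1.282) / 0.90 = 0.195, and 2.41 × 0.195 × (0.5 to 0.7) = 0.24 to 0.33 points, or 16% to 22% of 1.5.

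**4. What that does to power.** With 45 analysed per arm, the standard error of the difference is 2.41 × √(2/45) = 0.508. On the one-sided calculation that reproduces 45, power is Φ[(1.5 − bias)/0.508 − 1.645]. It is 90% with no bias, 80% at 0.24 and 74% at 0.33, if the bias runs against PRP.

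**5. What a model across visits recovers.** When loss depends on the recorded 3-month score, a likelihood analysis that keeps the earlier scores is unbiased (within 0.01 in simulation). When the worst 10% by 6-month pain itself are lost in one arm, the observed mean is off by 0.47. Using the 1- and 3-month scores still leaves 0.24 to 0.35, so half to three quarters of the bias remains. Adding the pre-infiltration score with the same assumed correlation leaves 0.22 to 0.33.

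**The case against.** The strongest reply is that nothing in the documents shows that bias will occur. The plan speaks of a possibility of loss, at the same rate in each group, and no section says that patients leave because pain returned. The remark in the Introduction concerns how long a corticosteroid effect lasts, not attendance; returning pain could equally bring patients back. This stands. Bias needs loss that is related to pain and unequal between arms, and the one-arm figures are upper-end cases.

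Three stronger readings are tempting, and the documents do not support them.

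- *That loss before infiltration would fall on the PRP arm alone*, because only that arm has a real blood draw and kit preparation. The schedule lists a confirmatory ultrasound for all patients, in the week before infiltration, under the stage that includes randomisation. A patient in either arm could therefore fail to reach infiltration, and no failure rate is given for any step.
- *That the plan states an analysis of infiltrated completers.* It says neither. It compares two groups, which are formed by randomisation, and a patient missing at 6 months still counts at 1 and 3. Restriction to patients with a value follows from the tests named; the handling of non-infiltrated patients is simply open.
- *That the problem is specific to 6 months.* No primary visit is named.

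It is also fair that a mixed model is not a complete cure, as step 5 of the working shows.

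What the reply does not remove is that the plan sets no analysis set and no way of using scores it already collects.

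**Conclusion.** The point holds as a conditional one. The allowance of 5 patients per group protects precision only, the stated tests discard recorded earlier scores for anyone missing the visit tested, and analysis as randomised is not stated.

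The resulting bias in the VAS difference ranges from 0 to 0.14 points in the two-arm scenarios examined, and reaches 0.24 to 0.33 points if the worst 10% leave one arm only. Its direction depends on which arm loses more painful patients. These sizes rest on the plan's SD, on assumed correlations of 0.5 to 0.7 and on assumed loss patterns; the documents give no split of loss by arm and no reasons for it. A reader should not conclude that the comparison will be biased, or that it must be biased against PRP. The change is worth making because it is cheap and uses data already planned.

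**What to change.** **Statistical analysis raised.** State that every randomised patient is analysed in the assigned arm. Replace the visit-by-visit tests for VAS, ASES, Constant and Pittsburgh with one repeated-measures mixed model per outcome. Use the pre-infiltration, 1-, 3- and 6-month values, arm-by-visit terms and an unstructured covariance. Name in advance the visit for the primary VAS contrast. Add one sensitivity analysis that worsens missing VAS values by 1 to 2 points, in one arm at a time, because the model removes only part of the bias when loss depends on pain arising after the last recorded visit.

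**Schedule - masking - intervention, Stage 4.** Keep scheduled assessments for every randomised patient, including anyone in either arm who is not infiltrated, for whom the planned infiltration date can serve as the starting point. Record the reason for leaving, by arm.

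**Cost.** Slightly more analysis and contact work, in the software already named, with no added patients. Telephone contact can recover VAS and self-reported items, but not goniometer mobility or the mobility parts of the function scores, so those outcomes will remain less complete.
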